[name]. med. [name]	Universitätsklinikum Bonn, Klinik für Kardiologie
[name]. med. [name]	Universitätsklinikum Heidelberg, Klinik für Neurologie
[name]. med. [name]	Universitätsklinikum Heidelberg, Klinik für Kardiologie
[name]. med. [name]	Klinikum der Universität München, Klinik für Neurologie
[name]. med. [name]	Klinikum der Universität München, Klinik für Kardiologie
[name]. med. [name]	Universitätsmedizin Göttingen, Klinik für Neurologie
[name]. med. [name]	Universitätsmedizin Göttingen, Klinik für Kardiologie
Dr. med. [name]	Universitätsklinikum Tübingen, Klinik für Neurologie

[name]. med. [name]	Universitätsklinikum Tübingen, Klinik für Kardiologie
[name]. med. [name]	Universitätsmedizin Greifswald, Klinik für Neurologie
[name]. med. [name]	Universitätsmedizin Greifswald, Klinik für Kardiologie
PD. Dr. med. [name]	Universitätsklinikum Leipzig, Klinik für Neurologie
[name]. med. [name]	Universitätsklinikum Leipzig, Klinik für Kardiologie
PD Dr. med. [name]	Universitätsklinikum Erlangen, Klinik für Neurologie
[name]. med. [name]	Universitätsklinikum Erlangen, Klinik für Kardiologie

Study type:

Multicenter observational prospective study with blinded endpoint evaluation

Background:

Cardiac troponins (i.e. I and T) are very sensitive and specific biomarkers used in clinical routine to detect cardiomyocyte damage. Elevation of cardiac troponins may indicate acute or chronic cardiomyocyte damage. An acute elevation of cardiac troponin with a dynamic change in serial measurements is often caused by an acute coronary syndrome due to a coronary culprit lesion¹. Interestingly, many patients with acute ischemic stroke also have elevated troponin levels². Depending on the assay and studied population, varying frequencies of elevated troponin levels in acute ischemic stroke patients have been reported in the literature. In acute ischemic stroke patients elevated troponin levels are associated with a higher rate of mortality and poor functional outcome^{3,4}.

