1.2 Objectives

The primary goal of the multicenter PRAISE study is to develop a diagnostic algorithm to better identify ACS as origin of troponin elevation in patients with an acute ischemic stroke. The primary hypothesis will test whether dynamic troponin levels (as compared to stable ones) indicate presence of ACS. The following hypotheses will be tested:

Primary hypothesis: A dynamic troponin elevation (>50% change at measurement after 3 hours) indicates an ACS in patients with an acute ischemic stroke. The change in troponin level (dynamic vs. stable after 3 hours) within patients with an acute ischemic stroke can be used to differentiate whether an ACS is present.

Endpoint: diagnosis of “ACS”, determined by an independent endpoint adjudication committee.

1. Secondary hypothesis: Stroke patients with dynamic troponin change have a worse functional outcome three or twelve months after the event in comparison to those with stable troponin.

Endpoints: Modified Rankin-Scale (mRS) after three and twelve months.

2. Secondary hypothesis: Stroke patients with dynamic troponin change have an increased risk for recurrence of cardiovascular events and a higher mortality rate in comparison to those with stable troponin.

Endpoints: Brain infarcts, transient ischemic attack (TIA), myocardial infarction (MI) and death as well as the combined endpoint thereof (MACE) during the acute inpatient stay, after three and twelve months.

In addition, in an exploratory approach we want to establish a combined rule-in/rule-out diagnostic algorithm to identify the subgroup of troponin-positive stroke patients in whom the diagnosis of ACS (i.e. type I vs. type II MI) vs. not is made by means of coronary angiography including stroke-specific cut-off values for troponin and other biomarkers, the value of ECG, echocardiography, clinical parameters, and combinations thereof.

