5.1.2 Secondary endpoints

Secondary endpoint analysed are performed in an explorative manner without adjustment for multiplicity.

The secondary endpoints

- Mortality
- cardiovascular events (stroke, TIA, Myocardial infarction)
- MACE (combined endpoint of death, recurrent stroke, TIA, myocardial infarction)

are time-to event data. Event rates at 1 week, 3- and 12-months follow-up are reported based on Kaplan-Meier estimators. Cox proportional hazards will be used to estimate hazard ratios (95%-CI) comparing the diagnostic groups (stable vs. dynamic) for mortality and cause-specific hazard ratios for cardiovascular events taking death as competing event into account.

The secondary endpoint

- mRS (measured at baseline, 1 week, 3- and 12-months follow-up)

is an ordinal scaled score which ranges from 0 (no symptoms) to 6 (death). This endpoint will be analysed by fitting a proportional-odds logistic regression model to calculate the common odds ratio (95%-CI) as a measure of the likelihood that individuals in the stable group would lead to lower scores on the mRS scale than would patients in the dynamic group.

During the course of the study it turned out that the imaging procedure and count of hospital admission were not realisable. Therefore, these endpoints cannot be analysed.

Table 1 gives an overview of measurement time points of all endpoints.

Endpoints	Time point			
	V1 < 72 h after admission	V2 < day 7 days	V3 3-months FU	V4 12-months FU
Primary endpoint				
Acute coronary syndrome (ACS)			X	
Secondary endpoints				
Cardiovascular events (stroke, TIA, death, MI)			X	X
MACE (combined endpoint)		X	X	X
Mortality		X	X	X
mRS	X	X	X	X
MI Type 1 / MI Type 2			X	

Table 1: Frequency and scope of study visits

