5.3 Additional analyses

The primary outcome analysis is repeated in the PP population. Additional analyses of the presence/absence of ACS in relation to presence/absence of dynamic troponin elevation include the calculation of further diagnostic accuracy measures like sensitivity and specificity together with the 95%-confidence interval.

A mediation analysis will be conducted to identify direct and indirect effects of the diagnostic group (dynamic vs. stable) and additionally peak troponin T in patients with available troponin T values (exposure variables) and the presence of ACS (yes vs. no) as well as presence of MI type 1 (yes vs. no) and in patients with ACS MI (Type 1 vs. Type 2) (mediator variables) on mortality and MACE (target outcome) using accelerated failure time models. This will be performed after unblinding of the diagnostic groups and analysed in an explorative manner.

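### SAP 5.3 places ACS downstream of troponin change, so the planned 'indirect effect' cannot be read as an effect of troponin change acting through ACS

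*SAP*

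**What the plan says.** The analysis is in SAP 5.3: "A mediation analysis will be conducted to identify direct and indirect effects of the diagnostic group (dynamic vs. stable" and so on. A second exposure is peak troponin T, in patients who have it. The mediators are "the presence of ACS (yes vs. no) as well as presence of MI type 1 (yes vs. no" and, among patients with ACS, MI type 1 against type 2. The effects are to be estimated "on mortality and MACE (target outcome) using accelerated failure time models". On its status the SAP adds: "This will be performed after unblinding of the diagnostic groups and analysed in an explorative manner". No confounders, causal diagram or identifying assumptions are given for it. The regressor list in SAP 5.3.2 is for the primary endpoint.

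On how the two variables are related, the protocol's Background says: "An acute elevation of cardiac troponin with a dynamic change in serial measurements is often caused by an acute coronary syndrome". SAP 1.2 gives the aim as to "develop a diagnostic algorithm to better identify ACS as origin of troponin elevation". The Background also names chronic cardiac disease, extracardiac disease and neurogenic myocardial injury as other sources of troponin elevation.

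SAP 5.1.2 defines the composite outcome as "MACE (combined endpoint of death, recurrent stroke, TIA, myocardial infarction".

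**The concern.** A mediator has to be something that the exposure changes. The order planned in SAP 5.3 is troponin change, then ACS, then death or MACE. The documents' own account runs from ACS to troponin change, and the whole study treats troponin as the test and ACS as the target condition.

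If ACS produces the troponin change and also worsens survival, it confounds the relation between troponin and survival. A mediation model fitted in the SAP's order will then attribute that confounded association to a path through ACS and call it an indirect effect. A larger sample does not remove the error; it only narrows the interval around the wrong quantity. What is at stake is the interpretation of one exploratory analysis: a reader could take its result as showing how a troponin change worsens survival.

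**Working it through.** **Step 1: the order in the documents.**

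| Role | SAP 5.3 | Rest of the documents |
|---|---|---|
| Troponin change | exposure (cause) | marker, often a result of ACS (Protocol, Background) |
| ACS | mediator (result of the exposure) | origin of the troponin elevation (SAP 1.2) |
| Death, MACE | outcome | outcome |

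Timing does not reverse this. Troponin is measured at 0 and 3 hours (SAP 2.1) and ACS is adjudicated within seven days of admission (SAP 1.2.1), but the date of adjudication is not the onset of disease. Even an ACS that began after 3 hours would not be an effect of the earlier troponin change.

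**Step 2: inputs.** The plan states no figure for the mediation analysis. The nearest is the sample size of 203, which shows the planning inputs. Take p0 = 6% in the stable group, an odds ratio of 4 and a dynamic share of 11/29 = 38%.

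- p1 = 4 × (0.06/0.94) / (1 + 4 × 0.06/0.94) = 0.203.
- The two-proportion formula (two-sided 5%, 80% power) gives 174, and 203 with continuity correction. The plan's figure is reproduced.
- Implied overall ACS rate: 0.379 × 0.203 + 0.621 × 0.06 = 11.4%.

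The pilot's culprit-lesion rate was higher, at 7/29 = 24%. With the same odds ratio and dynamic share, that rate corresponds to p1 = 0.401 and p0 = 0.144. Both cases are shown below.

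Assumptions that are not in the documents: exponential survival, 12% one-year mortality without ACS, ACS hazard ratio (HR) of 1.5 to 3, and no effect of troponin change on anything.

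**Step 3: what the planned analysis returns.** In an exponential AFT model ACS multiplies survival time by 1/HR. The indirect effect in the SAP's order is

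log time ratio = −ln(HR) × (p1 − p0),

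and the direct effect is a time ratio of 1. The true effect of troponin change is also 1.

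| ACS hazard ratio | 11.4% ACS (p1 − p0 = 0.143) | 24% ACS (p1 − p0 = 0.257) |
|---|---|---|
| 1.5 | exp(−0.405 × 0.143) = 0.94 | exp(−0.405 × 0.257) = 0.90 |
| 2 | exp(−0.693 × 0.143) = 0.91 | exp(−0.693 × 0.257) = 0.84 |
| 3 | exp(−1.099 × 0.143) = 0.85 | exp(−1.099 × 0.257) = 0.75 |

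Simulation agrees, apart from 0.86 rather than 0.85 at HR 3 with 11.4% ACS in small samples. The assumed mortality does not enter these ratios. It affects only how often they reach significance.

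**Step 4: how often it would look real.** At the 203 patients to be analysed, a Sobel test of the indirect effect was significant in about 4% of simulated trials at the mild end (11.4% ACS, HR 1.5) and about 71% at the strong end (24% ACS, HR 3). A repeat with a Weibull model gave 3% and 65%. At n = 5,000 the rate was 95% to 100%. The SAP does not name the test, and a joint-significance test gives higher rates at trial size.

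**Not simulated:** peak troponin T as exposure, and MI type 1 against type 2 as mediator. The argument about order in Step 1 covers peak troponin T as well.

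**The case against.** The other side has several good points.

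- **The protocol says often, not always.** A dynamic change may have other causes, and in the pilot 5 of the 11 patients with dynamic troponin had no culprit lesion. The illustration lets dynamic change occur without ACS but assumes that those other causes do not affect death. This stands as a limit on the illustration. It does not make ACS a result of troponin change. A reader might infer that the planned estimate reflects no causal effect of any kind. The documents do not support that: part of it reflects whatever effect ACS has on survival. What fails is its attribution to troponin change.
- **The analysis is labelled exploratory and the SAP states no causal conclusion.** A reader might infer that the trial will report troponin change as worsening survival through ACS. That would be a guess about future wording. The label, however, speaks to multiplicity and strength of evidence, not to the order of the variables, and direct and indirect effects are the stated target.
- **The remedy is partly relabelling.** Models without and then with ACS use much the same fits. This is true, but the confounders and the interpretation change, and those are what is missing.
- **MACE overlap.** Because MI appears without a qualifier in SAP 5.1.2, a reader might infer that the index MI counts both as mediator and as outcome. SAP 1.2.2 speaks of new events and the protocol's Functional Outcome section of recurrent MI, so that reading is not established. A clarification is enough.

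**Conclusion.** The point holds as one of interpretation. Taken with the documents' own account of ACS and troponin, the decomposition in SAP 5.3 does not estimate an effect of troponin change running through ACS. Under a null in which troponin does nothing, the indirect time ratio is about 0.94 to 0.85 with 11.4% ACS and 0.90 to 0.75 with 24% ACS, instead of 1.

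The departure from 1 needs only that ACS goes with troponin change and affects survival. On the latter, the Background cites an observational study in which coronary culprit lesions raised mortality after stroke. The size, and above all the significance rates, rest on the assumed hazard ratios, mortality and ACS rate and should be quoted only with them.

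The primary odds ratio, the sample size and the Cox comparison of groups in SAP 5.1.2 are untouched. The adjusted coefficients remain readable as associations. Severity: minor to moderate.

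**What to change.** 1. In SAP 5.3, replace the mediation analysis with AFT or Cox models for mortality and MACE. Fit the troponin group alone (and, separately, peak troponin T), then add ACS or MI type together with age, NIHSS, history of CHD, heart failure and eGFR. All of these covariates are already listed as regressors in SAP 5.3.2.
2. Report whether troponin carries prognostic information beyond ACS, as an association, without the terms direct effect, indirect effect or mediator.
3. Do not swap the roles so that troponin becomes the mediator. The documents treat troponin as an indicator of injury, not as a cause of death.
4. In SAP 5.1.2, carry over the qualifier new or recurrent for MI from SAP 1.2.2 and the protocol, so that the index MI does not count towards MACE.

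The cost is SAP wording, with no new data. The plan gives up a causal decomposition, which the documents do not support in this order. The adjusted mortality model will be imprecise: at the assumed 12%, 203 × 0.12 is about 24 deaths, somewhat more once ACS raises the risk, so its estimates should be read with their intervals.

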5.3.1 Subgroup analyses

Subgroup analyses with respect to the primary endpoint will be performed by the appropriate interaction tests. Each test will be performed at a significance level of alpha=5%.

Predefined subgroups will include:

- Gender (male/female)
- Age (dichotomized at 75 years)
- Renal failure (dichotomized at eGFR 60 ml/min)

5.3.2 Adjusted analyses

For the primary endpoint univariate and multiple logistic regression models will be fitted to the data to calculate unadjusted and adjusted odds ratios, including a series of baseline regressors:

- Age (continuous)
- Gender (dichotomous)
- Diabetes (dichotomous)
- Dyslipidemia (dichotomous)
- Renal failure (eGFR < 60 ml/min dichotomous)
- History of CHD (dichotomous)
- History of heart failure (dichotomous)
- History of atrial fibrillation/flutter (dichotomous)
- Haemoglobin (<12 g/dl for women, < 13 g/dl for men, dichotomous)
- Initial NIHSS (continuous)
- Heart rate (> 100/min, dichotomous)
- ECHO core lab: wall motion disturbance (dichotomous)
- ECG core lab findings: ACS typical changes (dichotomous)
- Peak troponin T value (continuous)

In an explorative analysis, an optimized multiple logistic regression model for the prediction of the primary endpoint is derived using the following procedure: in the first step, a multiple logistic regression model is established in a blinded manner, i.e. without taking troponin values into account, including relevant confounding variables into the model. In order to decide which variables are included in the model, clinical and statistical criteria are used, considering the distribution of the variables and their structure of missing values.

In the second step, variable selection is performed using backward selection.

In the last step, an unblinded analysis is performed, i.e. the troponin is included in the prognosis model to predict the primary endpoint. The final choice of variable selection method is based on the technical feasibility of the model, use of performance parameters, and clinical considerations. For the calculation of the ROC-AUC as performance measure, a 10-fold validation procedure will be performed.

The same procedure is applied in order to derive a prognostic model for the prediction of the presence of type 1 myocardial infarction as well as in those patients in whom ACS is present, for the prediction of type 1 vs. type 2 myocardial infarction as adjudicated by the EAC.

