Troponin (0 und 3 h)	X			
Clinical chemistry	X			
DZHK-Biobanking (optional)		X		
Study-specific examinations				
GRACE-Score	X			
Adverse Events	X	X	X	X
ECG	X	X		
Echocardiography (TTE)		X		
Coronary angiography		X		
endpoints				
Acute coronary syndrome (ACS)		X		
Recurrent cerebral ischemia, myocardial infarction, mortality		X	X	X

Table 1: PRAISE study procedures

Statistical analysis:

Sample size calculation:

The sample size calculation of the PRAISE study is based on data from the TRELAS study (Troponin elevation in acute stroke)⁹. In the TRELAS study, 7/29 (24%) of ischemic stroke patients with troponin elevation had a coronary culprit lesion and 11/29 (38%) of patients had dynamic troponin elevation (i.e. Δ change $> 50\%$). Of 11 patients with dynamic troponin elevation, 6 patients (54%) had a coronary culprit lesion. In patients without dynamic troponin elevation, only one patient (1/18=6%) had a coronary culprit lesion. Thus, the odds ratio of a dynamic troponin elevation for presence of a coronary culprit lesion was at 20.4. Due to the small sample size of the TRELAS study, we used the lower limit of the 80% confidence interval of the odds ratio (~4) to calculate the sample size for the PRAISE study. We assumed that the proportion of stroke patients with dynamic troponin elevation will be similar to the TRELAS study. Thus, 203 patients will have to be included to achieve a statistically significant result with a power of 80% (alpha=0.05). Since the TRELAS study only recruited patients with an initial hs-troponin T value > 50 ng/l (Roche Elecsys Assay), the proportion of patients with dynamic troponin elevation will likely be even higher in PRAISE. In order to compensate for cases of withdrawal of consent we plan to include 251 patients. The primary hypothesis will be tested using an intention-to-diagnose analysis by calculation of the odds ratio of acute coronary syndrome in patients with dynamic vs. stable troponin elevation. Secondary endpoints will be analyzed using the same statistical method.

In order to assess other predictors of acute coronary syndrome we will use the Chi-Square-test for dichotomous variables and the Wilcoxon-Test for continuous variables.

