2.3 Sample size

To be assessed for eligibility (n = 8,750 patients with ischemic stroke, thereof n = 1,250 with troponin elevation according to the inclusion criteria)

To be allocated to trial (n = 251)

To be analyzed (n = 203)

Full details of sample size calculation can be found in the study protocol.

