3.1 Confidence intervals and *P* values

All applicable statistical tests will be two-sided and will be performed using a 5% significance level. Analyses of secondary outcomes will be performed without adjustment for multiplicity. All confidence intervals presented will be 95% and two-sided.

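### The adjusted ACS model in SAP 5.3.2 has up to 15 slopes for about 23 to 49 expected events and no penalisation or separation rule; a Firth-type fit would remove most of the upward bias (minor)

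*SAP*

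**What the plan says.** SAP 5.3.2 (Adjusted analyses) announces: "For the primary endpoint univariate and multiple logistic regression models will be fitted to the data to calculate unadjusted and adjusted odds ratios". The regressors that follow are age, gender, diabetes, dyslipidaemia, renal failure, history of CHD, heart failure, atrial fibrillation or flutter, haemoglobin, initial NIHSS, heart rate, core-lab wall motion disturbance, core-lab ECG changes and peak troponin T. Each is continuous or dichotomous, so there are 14 terms with one degree of freedom each. The section names no estimator, penalty, exact method, events-per-variable check or rule for separation or non-convergence.

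On size, SAP 2.3 gives "To be analyzed (n = 203" and refers to the protocol, where the sample size calculation states: "203 patients will have to be included to achieve a statistically significant result with a power of 80% (alpha=0.05".

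The primary analysis (SAP 5.1.1) is the unadjusted diagnostic odds ratio for a change above 50%. The adjusted model comes under SAP 5.3, Additional analyses.

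**The concern.** Maximum-likelihood logistic regression pushes coefficients away from zero when events are few for the number of terms. It can also fail to give a finite estimate when covariates separate the outcome. An adjusted odds ratio for the primary comparison needs the dynamic/stable term as well as the 14 listed regressors, hence 15 slopes if all are fitted together. The protocol's statistical section named eight regressors, as examples. The SAP names 14 while the number to be analysed is still 203.

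Two of the regressors, ECG changes and wall motion, come from examinations that the adjudication committee uses to assign ACS (protocol, Study procedures), which makes separation more likely. At stake is the accuracy of a reported adjusted odds ratio. The trial's primary result is not at stake.

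**Working it through.** **Inputs**
- Two-sided test: "All applicable statistical tests will be two-sided and will be performed using a 5% significance level" (SAP 3.1). Power is 80% (protocol).
- Odds ratio: "we used the lower limit of the 80% confidence interval of the odds ratio (~4" (protocol).
- Stable-group rate: "only one patient (1/18=6%) had a coronary culprit lesion" (protocol).
- Overall rate and share dynamic: "7/29 (24%) of ischemic stroke patients with troponin elevation had a coronary culprit lesion and 11/29 (38%) of patients had dynamic troponin elevation" (protocol).
- Enrolment: "In order to compensate for cases of withdrawal of consent we plan to include 251 patients" (protocol).

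**Step 1: reproduce the planned 203.** Take p0 = 0.06. Then p1 = 4 × 0.06 / (0.94 + 4 × 0.06) = 0.24/1.18 = 0.2034. With allocation 38:62, the two-proportion formula with continuity correction gives 76.9, rounded up to 77 dynamic patients. The total is 77/0.38 = 202.6, or 203, an exact match. These inputs are therefore a sound reading of the planning scenario.

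**Step 2: expected events.**
- Planning scenario: 0.62 × 0.06 + 0.38 × 0.2034 = 0.1145, and 203 × 0.1145 = 23.2 events.
- TRELAS rate: 203 × 7/29 = 49.0 events.
- With all 251 patients: 28.7 and 60.6 events.

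**Step 3: events per slope (15 slopes).**
- 203 patients: 23.2/15 = 1.5 and 49.0/15 = 3.3.
- 251 patients: 28.7/15 = 1.9 and 60.6/15 = 4.0.

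**Step 4: simulation.** The true adjusted odds ratio is set to 4, with 38% dynamic. There are 11 binary covariates (prevalences 15–55%) and 3 continuous ones, with latent correlation 0.1. Covariate effects are none, moderate or strong. All of these are assumptions, because the documents give no such values. There were 1,000 replicates for maximum likelihood (ML) and 400 for Firth, at N = 203. ML medians are over fits that converged; coverage is for Wald-type 95% intervals.

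| Events | Covariate effects | ML median OR | ML estimates above 10 | ML failed fits | ML coverage | Firth median OR | Firth coverage |
|---|---|---|---|---|---|---|---|
| 23 | none | 4.81 | 11.6% | 4.5% | 0.940 | 3.78 | 0.968 |
| 23 | moderate | 4.95 | 17.1% | 1.6% | 0.921 | 3.88 | 0.945 |
| 23 | strong | 5.41 | 25.5% | 1.2% | 0.919 | 3.89 | 0.953 |
| 49 | none | 4.59 | 4.6% | 0% | 0.924 | 4.01 | 0.955 |
| 49 | moderate | 4.67 | 5.8% | 0% | 0.930 | 3.90 | 0.955 |
| 49 | strong | 4.76 | 10.3% | 0% | 0.921 | 4.02 | 0.965 |

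Relative bias of the ML median runs from 4.59/4 = 1.15 to 5.41/4 = 1.35. Firth gave a usable estimate in all 400 replicates of every scenario.

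**Step 5: sensitivity.**
- Rarer covariates (assumed: heart rate above 100 in 6%, ECG changes in 8%): ML failures rise to 14–30% at 23 events and about 2–4% at 49. ML medians are 4.6–5.0 and Firth medians 3.8–4.1.
- A separate 1,500-replicate run with another assumed covariate mix: ML medians 4.86 at 23 events, with 6.7% failures, and 4.59 at 49 events.
- All 251 patients: ML medians 4.4–4.9, failures 0–1.4%, Firth medians 3.6–4.2.

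**The case against.** The strongest reply is that the practical effect is small. The drift is about 0.3 standard deviations of the log odds ratio: ln(4.86/4) = 0.195 against 0.65. ML coverage is only a little below nominal. In runs with a true odds ratio of 1 the medians were 1.02–1.03 with coverage 0.94, so the bias does not create an effect from nothing. The 23 events come from a deliberately cautious odds ratio; at the observed 24% there are 49 events and no failed fits unless some covariates are rare. These rates describe culprit lesions, whereas adjudicated ACS in SAP 1.2.1 also includes unstable angina, so the event count could be higher. All of this stands, and it sets the severity. It does not remove the bias, which appears across the whole event range.

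Two further points stand as caveats: maximum likelihood is inferred from ordinary usage, and SAP 5.3.2 does not state outright that all terms enter one model.

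A reader might infer three stronger things that the documents do not support.
- *Backward selection starts from this overfitted model.* It does not. SAP 5.3.2 describes a separate exploratory model, built blinded to troponin from variables chosen on clinical and statistical grounds. Selection is applied to that model and troponin is added last. A 10-fold validation of its AUC is planned.
- *The adjusted odds ratio carries the trial's claim of added value.* No section says so. The primary inference is unadjusted, and SAP 5.3.3 assesses troponin change, alone and adjusted, through the ROC curve.
- *Missing covariates will shrink the fit to some much smaller number.* Complete-case loss would worsen the problem, but neither document gives a missingness rate, and SAP 5.2 plans multiple imputation as a sensitivity analysis when at least 5% is missing.

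**Conclusion.** The concern holds as a minor point. With up to 15 slopes on about 23 to 49 events, an ordinary maximum-likelihood fit would be expected to overstate a true adjusted odds ratio of 4 by roughly 15–35%. Some single estimates would exceed 10, and coverage would be 0.92–0.94. Failed fits are mainly a low-event problem: about 1–7% at 23 events, or 14–30% with rare covariates; at 49 events none with common covariates and up to about 5% with rare ones.

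The event range follows from the documents. The size of the bias rests on the assumed true odds ratio, the assumed covariate prevalences and effects, all 15 terms in one model, and maximum likelihood as the estimator. The primary diagnostic odds ratio is untouched.

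**What to change.** In SAP 5.3.2, state that the adjusted model for ACS will be fitted with Firth-type penalised likelihood and profile-likelihood confidence intervals, and that the number of events per parameter will be reported beside the estimates. State also which terms enter the model, including the dynamic/stable term. This handles separation without a further rule.

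The cost is a few lines of SAP wording; the method is available in R and Stata, both listed in SAP 5.4. The downside is slight shrinkage of the adjusted estimates (medians of 3.8–4.1 at N = 203 for a true value of 4). A shorter prespecified covariate list with a separation rule is an alternative. Shrinkage in the exploratory prediction model is optional.
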